#### **7.5. Electrocardiogram Results**

Summaries of investigator assessment of ECG readings will be provided for the Safety Analysis Set for each scheduled visit. No formal statistical testing is planned.

##### **7.5.1. Investigator Electrocardiogram Assessment**

A shift table of the investigators' assessment of ECG results at each visit compared with baseline values will be presented by treatment group using the following categories: normal; abnormal, not clinically significant; abnormal, clinically significant; or missing. The number and percentage of subjects in each cross-classification group of the shift table will be presented. Subjects with a missing value at baseline or postbaseline will not be included in the denominator for percentage calculation. No formal statistical testing is planned.

A by-subject listing for ECG assessment results will be provided by subject ID number and visit in chronological order.

**7.6. Other Safety Measures**

No additional safety measures are specified in the protocol.

**7.7. Changes from Protocol-Specified Safety Analyses**

There are no deviations from the protocol-specified safety analyses.

## **8. PHARMACOKINETIC (PK) ANALYSES**

### **8.1. PK Sample Collection**

#### **Part A (Cohorts 1-5 LEN PK sampling)**

Blood samples will be collected to determine LEN PK (and metabolites, if applicable) in plasma at the following time points relative to study drug dosing:

- Day 1: 0 (predose), 1, 2, 4, 8, 12, and 24 hours postdose
- Days 3, 4, 7, 8, 9, 10, 14, 29, 43, 57, 85, 113, 141, 169, 197, and 225 for a single anytime PK sample

#### **Part B (Cohorts 6-8 TAF PK sampling)**

Plasma PK samples will be collected to determine PK of TAF and its metabolite, TFV, at the following time points relative to study drug dosing:

- Day 1: 0 (predose), 0.5, 1, 2, 3, 4, 6, 8, 10, 12, 24, and 48 hours postdose
- Days 4, 5 (if possible), 6 (if possible), 7, 8, 9, and 10 at approximately the same time in the morning as predose on Day 1

PBMC PK samples will be collected to determine PK of TFV-DP at the following time points relative to study drug dosing:

- Day 1: 0 (predose), 1, 2, 4, 6, 8, 12, 24, and 48 hours postdose
- Days 4, 5 (if possible), 6 (if possible), 7, 8, 9, and 10 at approximately the same time in the morning as predose on Day 1

### **8.2. PK Analyses Related to PK Sampling**

#### **8.2.1. Estimation of PK Parameters**

PK parameters will be estimated using Phoenix WinNonlin® software using standard noncompartmental methods. The linear/log trapezoidal rule will be used in conjunction with the appropriate noncompartmental model, with input values for dose level, dosing time, plasma concentration, and corresponding real-time values, based on drug dosing times whenever possible.

All predose sample times before time-zero will be converted to 0.

For area under the curve (AUC), samples BLQ of the bioanalytical assays occurring prior to the achievement of the first quantifiable concentration will be assigned a concentration value of 0 to prevent overestimation of the initial AUC. Samples that are BLQ at all other time points will be treated as missing data in WinNonlin. The nominal time point for a key event or dosing interval ( $\tau$ ) may be used to permit direct calculation of AUC over specific time intervals. The appropriateness of this approach will be assessed by the PK scientist on a profile-by-profile basis.

Pharmacokinetic parameters such as  $\lambda_z$  and  $t_{1/2}$  are dependent on an accurate estimation of the terminal elimination phase of drug. The appropriateness of calculating these parameters will be evaluated upon inspection of PK data on a profile-by-profile basis by the PK scientist.

### 8.2.2. PK Parameters

PK parameters will be generated for all subjects for whom parameters can be derived. The analytes presented in [Table 8-1](#) will be derived if data are available.

**Table 8-1. Study Treatments and Associated Analytes**

Cohort	Treatment	Analyte
1	LEN 150 mg SC	LEN
2	LEN 50 mg SC	LEN
3	LEN 450 mg SC	LEN
4	LEN 20 mg SC	LEN
5	LEN 750 mg SC	LEN
6	TAF 200 mg tablet	TAF, TFV, TFV-DP
7	TAF 600 mg tablet	TAF, TFV, TFV-DP
8	Not conducted	

The analytes and parameters presented in [Table 8-2](#) will be used to evaluate the PK objectives of the study. The PK parameters to be estimated in this study are listed and defined in the PK Abbreviations section.

**Table 8-2. PK Parameters for Each Analyte**

Analyte	Parameters
LEN	AUC 0-t , AUC inf , AUC last , CL/F, $t_{1/2}$ , $\lambda_z$ , V z /F, C max , T max , C last , C D10 , T last
TAF	AUC 0-t , AUC inf , AUC last , CL/F, $t_{1/2}$ , $\lambda_z$ , V z /F, C max , T max , C last , T last
TFV	AUC 0-t , AUC inf , AUC last , $t_{1/2}$ , $\lambda_z$ , C max , T max , C last , T last
TFV-DP	AUC 0-t , AUC inf , AUC last , $t_{1/2}$ , $\lambda_z$ , C max , T max , C last , T last

### 8.3. Statistical Analysis Methods

#### 8.3.1. General Considerations

All PK analyses will be summarized based on the PK Analysis Set for the analyte of interest with the exception of the summary of TFV-DP which will be based on the PBMC PK Analysis set.

Individual subject concentration data and applicable individual subject PK parameters will be listed and summarized using descriptive statistics by treatment. Summary statistics (n, mean, SD, coefficient of variation [%CV], median, min, max, Q1, and Q3) will be presented for both individual subject concentration data by time point and individual subject PK parameters by treatment. Moreover, the geometric mean, 95% CI, and the mean and SD of the natural log-transformed values will be presented for individual subject PK parameter data.

Individual concentration data listings and summaries will include all subjects with concentration data. The sample size for each time point will be based on the number of subjects with nonmissing concentration data at that time point. The number of subjects with concentration BLQ will be presented for each time point. For summary statistics, BLQ values will be treated as 0 at predose and one-half of the lower LOQ for postdose time points.

Individual PK parameter data listings and summaries will include all subjects for whom PK parameter(s) can be derived. The sample size for each PK parameter will be based on the number of subjects with nonmissing data for that PK parameter.

The following tables will be provided for each analyte by treatment:

- Individual subject concentration data and summary statistics
- Individual subject plasma PK parameters and summary statistics

The following figures may be provided for each analyte by treatment:

- Mean ( $\pm$  SD) concentration data versus time (on linear and semilogarithmic scales)
- Median (Q1, Q3) concentration data versus time (on linear and semilogarithmic scales)

Mean and median postdose concentration values that are  $\leq$  LLOQ will not be displayed in the figures and remaining points connected.

PK sampling details by subject, including procedures, differences in scheduled and actual draw times, and sample age will be provided in listings. Individual data on determination of plasma half-life and corresponding regression correlation coefficient will also be listed.

The molecular weight of TFV-DP (447.17 g/mol) and the density of 5000 million cells/mL will be used in the conversion of concentration from ng/million cells to  $\mu\text{mol/L}$ ; where the value in ng/million cells \* (5000/447.17) results in the value in  $\mu\text{mol/L}$  or  $\mu\text{M}$ .

$$\frac{\text{ng}}{\text{million cells}} \times \frac{1 \text{ nmol}}{447.17 \text{ ng}} \times \frac{1 \mu\text{mol}}{1000 \text{ nmol}} \times \frac{5000 \text{ million cells}}{1 \text{ mL}} \times \frac{1000 \text{ mL}}{\text{L}} \times \frac{\mu\text{mol}}{\text{L}} \quad \mu\text{M}$$

### 8.3.2. Sensitivity Analyses

Sensitivity analysis may be conducted for the key PK analyses if the PK scientist identifies PK data as questionable. The sensitivity analysis will exclude specific data from analyses, if appropriate. If a sensitivity analysis is deemed necessary, a listing of the PK parameter(s) data being excluded, with associated reason(s) provided by the PK scientist, will be generated.

### 8.3.3. Changes from Protocol-Specified PK Analyses

The secondary endpoint of the correlation between  $C_1$  (concentration at Day 10) of LEN (Part A) and the maximum reduction of plasma HIV-1 RNA ( $\log_{10}$  copies/mL) from baseline through Day 10 will be replaced **CCI**

**CCI**

## **9. REFERENCES**

No references were used in this document.

## **10. SOFTWARE**

SAS® Software Version 9.4. SAS Institute Inc., Cary, NC, USA.

Phoenix WinNonlin® 7.0 Pharsight Corporation, Princeton, NJ, USA.

## 11. SAP REVISION

Revision Date (DD MMM YYYY)	Section	Summary of Revision	Reason for Revision

## 12. APPENDICES

- Appendix 1. Schedule of Assessments
- Appendix 2. Determining Missing and Virtual visits due to COVID-19
- Appendix 3. Programming Specifications

**Appendix 1. Schedule of Assessments**

	Screening a	Day 1 b, h	Day 2	Day 3 h	Day 4	CCI	Day 7 h	Day 8	Day 9	Day 10 h	Day 14	Day 29	Day 43	Day 57	Day 85 h	Day 113	Day 141	Day 169 h	Day 197	Day 225 h	Early Termination	
Written Informed Consent	X																					
Medical History	X																					
Complete Physical Examination	X	X																				X
Symptom Directed Physical Examination			X	X	X		X	X	X	X	X	X	X	X	X	X	X	X	X	X	X	
Vital Signs l (including weight)	X	X	X	X	X		X	X	X	X	X	X	X	X	X	X	X	X	X	X	X	X
12 lead ECG	X	X	X						X			X		X	X			X			X	
Height	X																					
Hematology f	X	X		X			X		X	X	X	X	X	X	X	X	X	X	X	X	X	X
Chemistry g	X	X		X			X		X	X	X	X	X	X	X	X	X	X	X	X	X	X
Estimated GFR c	X	X		X			X		X	X	X	X	X	X	X	X	X	X	X	X	X	X
Urinalysis and Urine Chemistry k	X	X		X			X		X	X	X	X	X	X	X	X	X	X	X	X	X	X
Urine Storage Sample		X		X			X		X	X	X	X	X	X	X	X	X	X	X	X	X	X
Serum Pregnancy Test e	X											X		X	X	X	X	X	X	X	X	X
Serum FSH i	X																					
Urine Pregnancy test		X																				
HBV, HCV Testing	X																					
CD4+ Cell Count	X	X							X			X	X	X	X	X	X	X	X	X	X	X
HIV 1 Genotyping/Phenotyping	X																					

	Screening a	Day 1 b,h	Day 2	Day 3 b	Day 4	CCI															Early Termination
						Day 7 h	Day 8	Day 9	Day 10 b	Day 14	Day 29	Day 43	Day 57	Day 85 h	Day 113	Day 141	Day 169 b	Day 197	Day 225 b		
HIV 1 capsid Genotype/Phenotype f	X								X												
HIV DNA genotyping														X			X		X		
Plasma HIV 1 RNA	X	X	X	X	X	X	X	X	X	X	X	X	X	X	X	X	X	X	X	X	X
Plasma Storage Sample		X	X	X	X	X	X	X	X	X	X	X	X	X	X	X	X	X	X	X	X
Intensive PK Plasma Collection (Part A)		X i																			
Single Anytime PK Plasma Sample (Part A) n				X	X	X	X	X	X	X	X	X	X	X	X	X	X	X	X	X	
PK Plasma Sample (Part B) o		X	X	X	X	X	X	X	X												
PBMC PK Samples (Part B) p		X	X	X	X	X	X	X	X												
CCI																					
LEN Administration (Part A)		X																			
TAF Administration (Part B)		X																			
B/F/TAF dispensation									X			X		X		X		X			
Adverse Events/Concomitant Meds	X	X	X	X	X	X	X	X	X	X	X	X	X	X	X	X	X	X	X	X	X

- a Screening evaluations must be completed within 42 days prior to Day 1.
- b Day 1 tests and procedures must be completed prior to administration of the dose of study drug
- c According to the Cockcroft Gault formula
- d Within 72 hours of permanently discontinuing study. Counsel subject regarding the importance of continuing a complete ARV therapy in accordance to standard of care, and refer patient to an appropriate HIV treatment facility.
- e Females of childbearing potential only
- f Hematology: CBC with differential and platelet count
- g Chemistries: Alkaline phosphatase, AST, ALT, GGT, total bilirubin, direct and indirect bilirubin, total protein, albumin, LDH, CPK, bicarbonate, BUN, calcium, chloride, creatinine, glucose, phosphorus, magnesium, potassium, sodium, uric acid, and amylase (reflex lipase testing if total amylase > 1.5 × ULN).
- h Fasting overnight (≥ 6 hours) required for Days 1, 3, 7, 10, 85, 169 and 225
- i FSH test is required for female subjects who have stopped menstruating for ≥ 12 months but do not have documentation of ovarian hormonal failure.
- j Vital signs blood pressure, pulse, respiration rate, and temperature, weight
- k Urinalysis and Urine Chemistry: including color & clarity, specific gravity, pH, glucose, ketones, bilirubin, urobilinogen, blood, nitrite, leukocyte esterase and microscopic (if microscopic elements are seen), urine protein, albumin, creatinine, phosphate, calcium, magnesium and uric acid
- l Part A: Serial blood samples to determine pharmacokinetics (PK) in plasma will be collected at the following time points relative to study drug dosing 0 (pre dose), 1, 2, 4, 8, 12 and 24 hours post dose.  
[REDACTED]
- n Part A: Single Anytime PK sample to be collected at the Day 3, 4, and 7 through 225 visits.
- o Part B: Plasma PK samples to be collected at the following time points relative to study drug dosing: 0 (pre dose), 0.5, 1, 2, 3, 4, 6, 8, 10, 12, 24 and 48 hours post dose; as well as at Days 4, CCI [REDACTED] 7, 8, 9 and 10 at approximately the same time in the morning as pre dose on Day 1.
- p Part B: PBMC PK samples to be collected at the following time points relative to study drug dosing: 0 (pre dose), 1, 2, 4, 6, 8, 12, 24 and 48 hours post dose, as well as at Days 4, CCI [REDACTED] 7, 8, 9 and 10 at approximately the same time in the morning as pre dose on Day 1.  
[REDACTED]
- r Part A: subjects require the HIV 1 capsid genotype/phenotype to confirm eligibility prior to randomization. Part B: the capsid genotype/phenotype will be completed for informational purposes, but it is not be required to confirm eligibility.

## **Appendix 2. Determining Missing and Virtual visits due to COVID-19**

This appendix describes the site collection of COVID-19 data as pertains to missed/virtual visits and the data processing algorithm used to determine which visits were missing and which visits were virtual.

### Data collection

A COVID-19 supplement to the eCRF Completion Guidelines (CCG) was provided by data management to instruct clinical trial sites with respect to data entry expectations pertaining to scenarios related to the COVID-19 pandemic. If a visit was missed, sites should enter “Visit missed due to COVID-19.” If a visit which was to be conducted in-person was conducted virtually, sites should enter “Virtual visit due to COVID-19.”

### Determination of Missed and Virtual visits

Natural Language Processing (NLP) was used to search the CRF comment fields to identify instances of “COVID-19” (or synonyms, see [Appendix Table 1](#)) and “Virtual” (or synonyms, see [Appendix Table 1](#)). The search terms are maintained in a global lookup and can be modified and/or corrected to tune the NLP model. For each comment field the following algorithm was applied:

**STEP 1:** Eliminate extraneous text from each comment field, e.g. “and”, “or”, “for”, etc. This is done using the list of extraneous terms given in [Appendix Table 2](#).

**STEP 2:** Check each of the remaining comment text strings against the “COVID-19” terms and “Virtual” terms with the Levenshtein distance, using SAS function COMPGED (Computes a generalized edit distance using the Levenshtein operations to compute/summarize the degree of difference between two text strings):

- i. If Levenshtein distance < 149 for any of the “COVID-19” terms then COVIDFL = 1, else COVIDFL = 0
- ii. If Levenshtein distance < 149 for any of the “Virtual” terms then VIRTFL = 1, else VIRTFL = 0

**STEP 3:** For any comments with COVIDFL = 1, assign “Missed visit” or “Virtual visit as follows

- i. IF COVIDFL = 1 and the visit date is missing then result is ‘Missed Visit’
- ii. IF COVIDFL = 1 and VIRTFL = 1 then result is ‘Virtual Visit’
- iii. Otherwise result is missing

**Appendix Table 1. Examples of search terms for “COVID-19” and “Virtual” used to identify missed and virtual visits.**

Search terms for “COVID-19”	Search terms for “Virtual”
COVID19	VIRTUAL
CORONA	TELEMED
CORONAVIRUS	TELEHEALTH
PANDEMIC	TELEPHONE
OUTBREAK	REMOTE
CRISIS	TELEMEDICINE
LOCKDOWN	TELECONSULTATION
QUARANTINE	TELEPHONICALLY
SHELTER	PHONE
	HOME VISIT
	ZOOM
	SKYPE

**Appendix Table 2. Examples of extraneous text terms to eliminate from the comment fields.**

a	down	in	she'd	until
about	during	into	she'll	up
above	each	is	she's	very
after	few	it	should	was
again	for	its	so	we
against	from	it's	some	we'd
all	further	itself	such	we'll
am	had	i've	than	were
an	has	let's	that	we're
and	have	me	that's	we've
any	having	more	the	what
are	he	most	their	what's
as	he'd	my	theirs	when
at	he'll	myself	them	when's
be	her	nor	themselves	where
because	here	of	then	where's
been	here's	on	there	which
before	hers	once	there's	while
being	herself	only	these	who
below	he's	or	they	whom
between	him	other	they'd	who's
both	himself	ought	they'll	why
but	his	our	they're	why's
by	how	ours	they've	with
could	how's	ourselves	this	would
did	i	out	those	you
do	i'd	over	through	you'd
does	if	own	to	you'll
doing	i'll	same	too	your
down	i'm	she	under	you're
	you've	yourself	yourselves	yours

### Appendix 3. Programming Specifications

- 1) For subjects who have previously screen failed, rescreened then enrolled into the study, the later date of rescreening will be used as the screening date. For subjects who have screen failed twice, the first screening date will be used as the screening date.
- 2) For enrolled subjects who have previously screen failed then rescreened, only eligibility criteria deviations from the rescreening visit were summarized in table and listings.
- 3) Body mass index (BMI)

BMI will be calculated only at baseline as follows:

$$\text{BMI} = (\text{weight [kg]}) / (\text{height [meters]}^2)$$

Baseline height and weight will be used for this calculation.

- 4) Please note, “Not Permitted”, “Unknown”, or missing categories will be excluded for percentage calculation. An exception is for Mode of infection (HIV Risk Factors), where “Unknown” will be included for percentage calculation, since a subject may fit more than 1 HIV risk factor, therefore percentage may add to more than 100%.

#### 5) Graded Laboratory Abnormalities Summary

The following labels will be used for treatment-emergent laboratory abnormalities and treatment-emergent Grade 3 or 4 laboratory abnormalities summary tables and listings:

Battery	Lab Test Label Used in I-labtox Listing	Toxicity Direction	Lab Test Label Used in t-labtox Table
Hematology	Hemoglobin	Decrease	Hemoglobin (Decreased)
	Neutrophils	Decrease	Neutrophils (Decreased)
	Platelets	Decrease	Platelets (Decreased)
	WBC	Decrease	WBC (Decreased)
Chemistry	Albumin	Decrease	Albumin (Decreased)
	Alkaline Phosphatase	Increase	Alkaline Phosphatase (Increased)
	ALT	Increase	ALT (Increased)
	Amylase	Increase	Amylase (Increased)
	AST	Increase	AST (Increased)
	Bicarbonate	Decrease	Bicarbonate (Decreased)
	Corrected Calcium	Increase	Corrected Calcium (Hypercalcemia)
	Corrected Calcium	Decrease	Corrected Calcium (Hypocalcemia)
	Creatine Kinase (CK)	Increase	Creatine Kinase (Increased)
	Creatinine	Increase	Creatinine (Increased)
	GGT	Increase	GGT (Increased)

Battery	Lab Test Label Used in I-labtox Listing	Toxicity Direction	Lab Test Label Used in t-labtox Table
	Lipase	Increase	Lipase (Increased)
	Magnesium	Decrease	Magnesium (Hypomagnesemia)
	Phosphate	Decrease	Phosphate (Hypophosphatemia)
	Serum Glucose (Fasting)	Increase	Serum Glucose (Fasting, Hyperglycemia)
	Serum Glucose (Fasting)	Decrease	Serum Glucose (Fasting, Hypoglycemia)
	Serum Glucose (Nonfasting)	Increase	Serum Glucose (Nonfasting, Hyperglycemia)
	Serum Glucose (Nonfasting)	Decrease	Serum Glucose (Nonfasting, Hypoglycemia)
	Serum Potassium	Increase	Serum Potassium (Hyperkalemia)
	Serum Potassium	Decrease	Serum Potassium (Hypokalemia)
	Serum Sodium	Increase	Serum Sodium (Hypernatremia)
	Serum Sodium	Decrease	Serum Sodium (Hyponatremia)
	Total Bilirubin	Increase	Total Bilirubin (Hyperbilirubinemia)
	Urea Nitrogen (BUN)	Increase	Urea Nitrogen (Increased)
	Uric Acid	Increase	Uric Acid (Hyperuricemia)
	Uric Acid	Decrease	Uric Acid (Hypouricemia)
Urinalysis	Urine Glucose	Increase	Urine Glucose (Glycosuria)
	Urine Protein	Increase	Urine Protein (Proteinuria)
	Urine RBC (Quantitative)	Increase	Urine RBC (Hematuria, Quantitative)

- 6) PK concentration analysis visit names will follow day/hour labeling combinations defined in the protocol Section 6.6.1 (i.e. Day 1 48 hours post dose).
- 7) Clarification for “Pharmacokinetic Sampling Details and Concentrations” listings

“Sample age” will be added in this listing, defined as the duration in days between sample collection date and assay date, ie,  $\text{sample age} = \text{assay date} - \text{sample collection date} + 1$ .

Scheduled PK sampling time for intensive PK samples at predose is 5 mins prior to dosing time.

SAMTIME is calculated as the duration in hours between the dosing time before sample collected and sample collection time, except for intensive PK samples at predose. SAMTIME for intensive PK samples at predose is calculated as the duration in hours between the dose time on the same day (ie, right after the predose sample collection) and sample collection time.

- 8) PK parameters at the individual subject level should be displayed with the following reported decimal places

LambdaZ, r2, r2 adj, and CORRXY: 3 decimal places

t1/2, Tlast, Tmax, BEGHOUR and ENDFHOUR: 2 decimal places

AUC0 D10, AUCtau, AUClast, AUCinf, %AUCexp, Vz/F, CL/F, CLss/F, Cmax, Clast, Ctau, AR\_AUC, and AR\_Cmax: 1 decimal place

NPOINTS: 0 decimal places

- 9) Concomitant nonstudy-drug ARV medications (ie, ARV medications other than study drug that are taken on or after first dose date) will be flagged in “Antiviral Medication” listings.

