6.6.2. Urine Samples

Urine samples will be collected for the following laboratory analyses at every study visit, unless otherwise specified:

- Urinalysis and urine Chemistry: including color & clarity, specific gravity, pH, glucose, ketones, bilirubin, urobilinogen, blood, nitrite, leukocyte esterase and microscopic (if microscopic elements are seen), urine protein, albumin, creatinine, phosphate, calcium, magnesium and uric acid (**All visits except Days 2, 4, 8 and 9**)
- Urine pregnancy test (females of childbearing potential only). If the test is positive, confirmatory serum test should be sent and study drug dosing should be delayed until results obtained (**Day 1**)
- Urine storage (**All visits except Screening, Days 2, 4, 8 and 9**)

CCI

CCI

6.7. Management of Virologic Failure after Initiation of B/F/TAF on Day 10

Subjects who experience either suboptimal virologic response (SVR) or virologic rebound (VR) after initiating B/F/TAF, as defined below, will be considered to have virologic failure.

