8.6.3. Laboratory Evaluations

Selected laboratory data will be summarized using only observed data. Data and change from baseline at all scheduled time points will be summarized.

Graded laboratory abnormalities will be defined using the grading scheme defined in Grading of laboratory abnormalities attached in [Appendix 4](#).

Incidence of treatment-emergent laboratory abnormalities, defined as values that increase at least 1 toxicity grade from baseline at any time post baseline, will be summarized by treatment group. If baseline data are missing, any graded abnormality (ie, at least a Grade 1) will be considered treatment emergent. The post baseline maximum toxicity grade will be summarized by laboratory parameter.

Laboratory abnormalities that occur before the first dose of study drug will be included in a data listing.

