Alkaline Phosphatase	1.25 to 2.50 × ULN	> 2.50 to 5.00 × ULN	> 5.00 to 10.00 × ULN	> 10.00 × ULN
Total Amylase	> 1.0 to 1.5 × ULN	> 1.5 to 2.0 × ULN	> 2.0 to 5.0 × ULN	> 5.0 × ULN
Pancreatic Amylase	> 1.0 to 1.5 × ULN	> 1.5 to 2.0 × ULN	> 2.0 to 5.0 × ULN	> 5.0 × ULN
Lipase	> 1.0 to 1.5 × ULN	> 1.5 to 3.0 × ULN	> 3.0 to 5.0 × ULN	> 5.0 × ULN
Albumin Pediatrics <16 years	-	2.0 to < LLN g/dL 20 to < LLN g/L	< 2.0 g/dL < 20 g/L	NA
≥ 16 years	3.0 g/dL to < LLN 30 g/L to < LLN	2.0 to < 3.0 g/dL 20 to < 30 g/L	< 2.0 g/dL < 20 g/L	NA

URINALYSIS				
	Grade 1	Grade 2	Grade 3	Grade 4
Hematuria (Dipstick)	1+	2+	3-4+	NA
Hematuria (Quantitative) See Note below				
Females	>ULN - 10 RBC/HPF	> 10-75 RBC/HPF	> 75 RBC/HPF	NA
Males	6-10 RBC/HPF	> 10-75 RBC/HPF	> 75 RBC/HPF	NA
Proteinuria (Dipstick)	1+	2-3+	4+	NA
Proteinuria, 24 Hour Collection				
Adult and Pediatric ≥ 10 Years	200 to 999 mg/24 h	>999 to 1999 mg/24 h	>1999 to 3500 mg/24 h	> 3500 mg/24 h
Pediatric > 3 Mo to < 10 Years	201 to 499 mg/m ² /24 h	>499 to 799 mg/m ² /24 h	>799 to 1000 mg/m ² /24 h	> 1000 mg/ m ² /24 h
Glycosuria (Dipstick)	1+	2-3+	4+	NA

Notes:

- Toxicity grades for Quantitative and Dipstick Hematuria will be assigned by Covance Laboratory, however for other laboratories, toxicity grades will only be assigned to Dipstick Hematuria.
- With the exception of lipid tests, any graded laboratory test with a result that is between the LLN and ULN should be assigned Grade 0.
- If the severity of a clinical AE could fall under either one of two grades (eg., the severity of an AE could be either Grade 2 or Grade 3), select the higher of the two grades for the AE.

CARDIOVASCULAR				
	Grade 1	Grade 2	Grade 3	Grade 4
Cardiac Arrhythmia (general) (By ECG or physical exam)	Asymptomatic AND No intervention indicated	Asymptomatic AND Non-urgent medical intervention indicated	Symptomatic, non-life-threatening AND Non-urgent medical intervention indicated	Life-threatening arrhythmia OR Urgent intervention indicated
Cardiac-ischemia/Infarction	NA	NA	Symptomatic ischemia (stable angina) OR Testing consistent with ischemia	Unstable angina OR Acute myocardial infarction
Hemorrhage (significant acute blood loss)	NA	Symptomatic AND No transfusion indicated	Symptomatic AND Transfusion of ≤ 2 units packed RBCs (for children ≤ 10 cc/kg) indicated	Life-threatening hypotension OR Transfusion of > 2 units packed RBCs indicated (for children ≤ 10 cc/kg) indicated

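### The SAP's graded-laboratory tables take haematuria only from quantitative urine RBC and leave out dipstick haematuria, an undeclared gap of unknown but probably small size

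*SAP*

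**What the plan says.** SAP Appendix 3, item 5 introduces its list this way: "The following labels will be used for treatment-emergent laboratory abnormalities and treatment-emergent Grade 3 or 4 laboratory abnormalities summary tables and listings". The urinalysis battery has three rows: urine glucose, urine protein and "Urine RBC (Hematuria, Quantitative".

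The urinalysis section of Protocol Appendix 4 grades haematuria by two methods. One is "Hematuria (Dipstick", with 1+ as Grade 1, 2+ as Grade 2 and 3-4+ as Grade 3. The other is a red-cell count per high-power field. The notes to that section say "Toxicity grades for Quantitative and Dipstick Hematuria will be assigned by Covance Laboratory", and continue "however for other laboratories, toxicity grades will only be assigned to Dipstick Hematuria".

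The urinalysis components in Protocol 6.6.2 include "blood, nitrite, leukocyte esterase and microscopic (if microscopic elements are seen". Blood carries no condition there; microscopy does.

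Protocol 8.6.3 sets the rule for the tables: "Graded laboratory abnormalities will be defined using the grading scheme defined in Grading of laboratory abnormalities attached in" Appendix 4. It then calls for treatment-emergent incidence by treatment group. SAP 7.7 reports: "There are no deviations from the protocol-specified safety analyses".

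**The concern.** The SAP tabulates the haematuria measure that depends on microscopy and on which laboratory was used. It leaves out the one that is graded at any laboratory. A participant whose urine blood rises from negative to 2+, with no graded red-cell count, would add nothing to the haematuria row.

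Graded laboratory abnormalities are a secondary endpoint (Protocol 3.1 and 8.1.3). Part A tests a new long-acting injectable. Part B gave single TAF doses of 200 and 600 mg (SAP 1.2), and Protocol 1.5.2 describes safety above 125 mg as unknown. With groups of 6 to 10, each participant counted or not counted moves a percentage visibly. The narrowing is neither explained nor listed as a change from the protocol.

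**Working it through.** The plan states no figure for this point, so the check compares lists and then works out the consequences.

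**1. Rows in SAP Appendix 3, item 5.** Haematology 4 + chemistry 26 + urinalysis 3 = 33 rows. Hypoglycaemia appears twice (fasting and nonfasting) but has one adult scale in Appendix 4, so the distinct test directions number 33 − 1 = 32.

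**2. Applicable tests in Protocol Appendix 4.** Keep the laboratory scales that apply to HIV-positive adults and whose test is collected under Protocol 6.6.1 or 6.6.2. This drops, for example, the CD4 and lymphocyte scales (HIV-negative only) and lipids, clotting tests and 24-hour urine protein (not collected). What remains is haematology 4 + chemistry 25 + urinalysis 4 (dipstick haematuria, quantitative haematuria, proteinuria, glycosuria) = 33. The match with the 33 rows in step 1 is a coincidence.

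**3. Difference.** 33 − 32 = 1: dipstick haematuria. No item 5 entry is absent from Appendix 4.

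**4. When a dipstick-positive sample reaches the haematuria row**, from the Appendix 4 note and Protocol 6.6.2:

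| Laboratory | Red-cell count reported | Dipstick grade | Quantitative grade | In the SAP row |
|---|---|---|---|---|
| Named one | Yes | Yes | Yes | Yes |
| Named one | No | Yes | No | No |
| Any other | Yes or no | Yes | No | No |

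This reads the unconditional listing of blood in 6.6.2 as a dipstick result at each urinalysis. That is a fair reading, but 6.6.2 does not mention a dipstick.

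**5. Occasions.** Part A has 17 post-dose visits. Urinalysis is omitted on Days 2, 4, 8 and 9, so 17 − 4 = 13 remain, of which 3 (Days 3, 7 and 10) fall by Day 10. Part B has the same 13. The optional Days 5 and 6 could raise that to 15, because 6.6.2 does not exclude them.

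**6. What one participant is worth.** If every participant in the group has a post-baseline value: 1/6 = 16.7% in a GS-6207 group, 1/8 = 12.5% in a TAF group, 1/10 = 10% in pooled placebo. These figures say nothing about how likely a missed case is.

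**7. Side effect on the printed row (illustration only).** SAP 7.2.2.2 uses participants with nonmissing post-baseline values as the denominator. Suppose absent microscopy counts as missing, which the SAP does not settle. One graded case then gives 1/m, where m is the number of participants with a count: in a group of 6, 1/2 = 50% if two have one and 1/6 = 17% if all do. The documents give no value for m.

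**The case against.** Item 5 supplies labels. It is not worded as an exclusion rule, and SAP 7.2.2 applies the whole grading scale to laboratory results. Haematuria can be seen as one abnormality with two grading methods, and Protocol 8.6.3 does not promise a row for each. Quantitative grading also has a rationale: Appendix 4 grades it separately by sex, and dipstick blood is less specific. The row label tells the reader which method was used.

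Part of this stands. The choice could be defended if it were stated. But the list otherwise matches every applicable collected test, and a programmer following it would produce no dipstick row. Nor does the SAP avoid dipstick grading in general: the glucose and protein rows have only dipstick scales in Appendix 4, apart from a 24-hour protein collection that this study does not make. The word *selected* in Protocol 8.6.3 governs the summaries of observed data, not the incidence sentence.

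Two stronger readings are tempting.

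- *The haematuria row might hold no graded values in any group.* That follows only if the named laboratory was not used, and the documents do not identify the study laboratory. The SAP was written after conduct was partly known: SAP 1.2 records that Cohort 8 was not initiated, and SAP 2.1 reports interim analyses in the past tense. Its choice of a quantitative label suggests that quantitative grades existed, though it does not prove it.
- *Dipstick haematuria might vanish from the report.* It need not. SAP 7.2 flags graded or out-of-range urinalysis values in by-subject listings. SAP 7.2.2.2 summarises categorical results by visit. Haematuria reported as an adverse event enters the tables of SAP 7.1.6. None of these gives treatment-emergent laboratory incidence by worst grade, and an unreported dipstick positive would not reach the adverse event tables.

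It is also fair to say that microscopy may well be done in most samples containing red cells, since 6.6.2 ties it to elements being seen. The loss may therefore be small.

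**Conclusion.** The concern holds as a minor point. Dipstick haematuria is the only applicable, collected, Appendix 4 graded test without a row in SAP Appendix 3, item 5, and SAP 7.7 does not declare the omission. A participant with graded dipstick blood and no graded red-cell count would not be counted in the treatment-emergent or Grade 3 or 4 laboratory tables.

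How many participants this affects cannot be derived. It depends on which laboratory analysed the urine and on how often a dipstick-positive sample had no count. The conclusion rests on reading item 5 as the working specification for those tables and on dipstick blood being available at each urinalysis. The results stay in the database, and no efficacy analysis is touched.

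**What to change.** In SAP Appendix 3, item 5, add a urinalysis row: `Urine Blood (Dipstick) | Increase | Urine Blood (Hematuria, Dipstick)`, graded by Protocol Appendix 4. Carry it into the treatment-emergent table, the separate up-to-Day-10 table and the Grade 3 or 4 table, and keep the quantitative row alongside it.

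If the sponsor prefers quantitative results alone, SAP 7.7 should say so with the reason, confirm that the named laboratory analysed all urine, and state how participants without microscopy enter the baseline grade and the denominator.

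The cost is one line of SAP text and one row in existing tables, from data already collected. The small downside is that dipstick blood is less specific, so some benign positives will be shown.
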